6.1 CRITERIA FOR SUBJECT ELIGIBILITY

6.2 Subject Inclusion Criteria

A patient will be eligible for androgen receptor expression testing if the following criteria are met:

- Pathologically confirmed adenocarcinoma of the breast which is ER(-) and PR(-).
- Non-measurable or Measurable, metastatic disease

IRB#: 07-022A(13)

A patient will be eligible for participation in the therapeutic trial if the following criteria are met:

- Androgen receptor expression testing confirms that the patient's tumor is ER(-)/PR(-) /AR(+). ER, PR and AR are considered positive if greater than 10% of cell nuclei are immunoreactive. Receptor testing may be performed on either primary tumor specimen or tissue from a metastatic site.
- Prior neo-adjuvant or adjuvant chemotherapy is allowed. Any number of chemotherapy regimens are allowed for metastatic disease. There is no restriction on prior treatment with hormonal agents.
- Prior treatment with trastuzumab must have been given if patient has Her2/neu positive disease (defined as IHC=3+ or FISH amplified).
- At least 2 weeks since prior cytotoxic chemotherapy. Patients should have recovered from all acute effects of such therapy.
- Absence of active brain metastatic disease or leptomeningeal disease. If patient has a history of brain metastases, lesions must be stable for at least 3 months (as documented by either head CT or brain MRI).
- At least 4 weeks from major surgery with full recovery
- ECOG performance status 0-1
- Age 18 years or greater
- Laboratory parameters as follows:
 - \circ ANC $\geq 1.5 \times 10^9$ cells/L
 - \circ Platelets $\geq 100 \text{ x } 10^9 \text{ cells/L}$
 - $\circ \quad Hgb \geq 9g/dL$
 - AST (SGOT), ALT (SGPT) ≤ 2.5 x upper limit of normal range (ULN); total bilirubin ≤ 1.5 x ULN; alkaline phosphatase ≤ 2.5 x ULN (unless bone metastases are present in the absence of liver metastases), creatinine ≤ 1.5 mg/dL
- If female of childbearing potential, pregnancy test is negative
- If fertile, the patient agrees to use an effective method to avoid pregnancy for the duration of the study
- Informed consent has been obtained

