9.1 TREATMENT/INTERVENTION PLAN

9.2 Agent Administration

Treatment will be administered on an outpatient basis. Bicalutamide is administered orally at 150 mg (three 50mg tablets) on a continuous daily schedule. A cycle length consists of 4 weeks of therapy. Please refer to the Time and Events Calendar (Section 10) for a detailed description of required tests. Radiographic tumor assessment will take place every 3 cycles.

Expected adverse events for bicalutamide are described in Section 5.0. Appropriate dose modifications for bicalutamide are described in Section 4.2 and Section 11.2. Two 50mg dose reductions are permitted per protocol. A treatment delay of up to 2 weeks is permitted. Therapy will continue until disease progression or unacceptable toxicity.

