10.0 EVALUATION DURING TREATMENT/INTERVENTION

Day 0 and every 4 weeks (+/- 5 days), the following clinical and laboratory assessments must be done prior to continuation of treatment with bicalutamide:

- History and physical examination, including:
 - Vital signs
 - ECOG performance status
 - o Weight
 - Concomitant medications
- Laboratory assessments, including: (screening labs can be used as Day 0 labs)
 - CBC with differential and platelet count
 - Comprehensive metabolic panel (Na, K, Cl, CO2, BUN, Creatinine, Ca, Glucose, Total Protein, Albumin, Alkaline Phosphatase, Total Bilirubin, AST and ALT)
- Adverse Event Evaluation (toxicity assessment using the NCI CTC version 3)
- Blood for correlative study of hormonal levels including estradiol, total testosterone, free testosterone, and sex-hormone binding globulin will be performed at baseline, after Cycle #1 and at the end of study. (See further description below)

Every 12 weeks (+/- two weeks), tumor assessments will be performed. Patients with measurable disease will be evaluated for complete response (CR), partial response (PR), stable disease (SD) or progressive disease (PD) using RECIST criteria, using the same modality of imaging performed at baseline. Patients with non-measurable disease will be evaluated for either stable disease or progressive disease. Responders and stable disease patients will continue on study unless they develop unacceptable toxicity. Progressive disease or unacceptable toxicity (after a maximum of two dose reductions) will be the criteria for treatment failure and discontinuation from the study.

Response assessment will include:

- Radiologic scans of disease sites (e.g. CT scan of chest, abdomen and pelvis and PET or bone scan if there are bone lesions identified on pre-study bone imaging)
- Measurement of all target lesions that are followed by physical examination
- Patients achieving a CR or PR must have confirmation of response at least 4 weeks following the initial response determination.
- End-of-Study (EOS) Evaluation: At the time patients are removed from study, laboratory and clinical evaluations to assess adverse events (AEs) will be performed. Serum hormone panel including estradiol, free and total testosterone and serum hormone binding globulin will be collected. Radiologic studies for antitumor response will be repeated if they have not been performed within the previous 28 days.

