- Adverse Event Resolution Follow-up: Any AE that started anytime beginning from the

IRB#: 07-022A(13)

time the patient has registered, and up to 30 days after the last dose of bicalutamide, must be followed until the AE has resolved or stabilized.

Correlative study methods:

All correlative studies will be performed for the purpose of exploratory analysis. Correlative study will include immunohistochemical (IHC) analysis of proteins representing the ER(-) Class A and Basal subtypes, including ALCAM, SPDEF and CK 5/6. IHC analysis will be performed using preexisting formalin fixed paraffin embedded biopsy or excision tissue from cancer sites. An exploratory analysis will be performed to correlate IHC expression profile and response to bicalutamide. In addition, the effect of bicalutamide administration on serum hormone level will be investigated. Estradiol, free and total testosterone and serum hormone binding globulin will be measured at baseline, after cycle #1 and at the end of study to describe changes in these circulating hormones in response to androgen blockade in women.

Paraffin embedded tissue from primary tumor or metastatic site which has tested AR+ will be requested from participating patients. These tumor blocks, if available, will be collected and stored for the purpose of future correlative studies to understand the biology of AR+ breast cancer.

IRB#: 07-022A(13)

Time and Events Schedule

Study Parameter	Prestudy	Every cycle ^a	Every 3 cycles	Study Termination (EOS)	AE resolution
Informed consent ^b	X				
History	Х				
Concomitant medications	Х	Х		Х	
Physical examination	Х	Х		Х	Х
Vital signs	Х	Х		Х	Х
Height and body weight	Х	Xc		Xc	
ECOG performance status	Х	Х		Х	Х
Adverse Event Evaluation		Х		Х	
Disease Status					
Tumor assessment (clinical)		\mathbf{V}^{d}			
Tumor assessment with CT scan	Х		Xe	Х	
Tumor assessment with PET or Bone scan ^g	Х		Х	Х	
Toxicity assessment (by patient and by physician)		Х		Х	
CBC with differential and platelet count	Х	Х		Х	
Comprehensive blood panel (including chemistries and liver function tests) ^h	X	Х		Х	X
Tumor Markers (Ca 15-3 & CEA, or CA 27- 29)	Х	Х		Х	
Estradiol, total testosterone, free testosterone, sex-hormone binding globulin *Only after Cycle #1.	Х	X*		Х	
Pregnancy test	Xf				

^a one cycle is equal to 4 weeks

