11.2.2 Serious adverse event

A serious adverse event is an AE occurring during any study phase (*eg*, run-in, treatment, washout, follow-up), and at any dose of the investigational product, comparator or placebo, that fulfills one or more of the following criteria:

- results in death
- is immediately life-threatening (defined as an immediate risk of death from the event as it occurred)
- requires in-patient hospitalization or prolongation of existing hospitalization (Exception: hospitalization for elective treatment of a pre-existing condition that did not worsen during the study is not considered an adverse event. NOTE: Complications that occur during hospitalization are adverse events and if a complication prolongs hospitalization, then the event is serious)
- results in persistent or significant disability or incapacity
- is a congenital abnormality or birth defect
- is an important medical event that may jeopardize the subject or may require medical intervention to prevent one of the outcomes listed above.
- Is a Grade 4 laboratory abnormality.

The causality of SAEs (their relationship to study treatment) will be assessed by the investigator(s).

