13.0 CRITERIA FOR REMOVAL FROM STUDY

Patients will be removed from the study if any of the following conditions apply:

- intercurrent illness which would in the judgment of the investigator effect assessments of clinical status to a significant degree or require discontinuation of drug;
- unacceptable toxicity;
- progressive disease;
- request by the patient to withdraw;
- patient non-compliance with protocol;
- irradiation of an indicator lesion during the trial;
- if at the discretion of the investigator continued treatment would be harmful or ineffective.

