17.2.5 Sponsor Notification of Post-Study Serious Adverse Events

The investigator should notify AstraZeneca of any death or SAE occurring after a patient has withdrawn from the study, when such death or SAE may reasonably be related to medication used in the study. However, investigators are not obligated to actively seek adverse events in former study participants.

Adverse events will be recorded on the case report forms by the investigator using verbatim terms that best describe the event. Grading of severity will be based upon the NCI CTCAE version 3.0. All adverse events will be coded to a MedDRA term by the sponsor. All MedDRA terms will then be mapped into the appropriate NCI CTCAE version 3.0 term.

Adverse events will be analyzed in terms of treatment-emergent AEs defined to be any AEs that begin or worsen in intensity after study drug initiation through 30 days after the last dose of study drug.

The incidence of all adverse events (all AEs regardless of causality) and all treatment related adverse events (those AEs thought to be possibly, probably or definitely related to study drug) will be summarized by NCI CTCAE version 3.0 term and maximum grade. The incidence of Serious Adverse Events (SAEs) and AEs that lead to discontinuation of study drug will also be summarized. Listings of patients that discontinued study drug due to an adverse vent, patients with SAEs and deaths will be presented. Patients with SAEs will be described by narrative.

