18.1 INFORMED CONSENT PROCEDURES

Before protocol-specified procedures are carried out, consenting professionals will explain full details of the protocol and study procedures as well as the risks involved to participants prior to their inclusion in the study. Participants will also be informed that they are free to withdraw from the study at any time. All participants must sign an IRB/PB-approved consent form indicating their consent to participate. This consent form meets the requirements of the Code of Federal Regulations and the Institutional Review Board/Privacy Board of this Center. The consent form will include the following:

IRB#: 07-022A(13)

- 1. The nature and objectives, potential risks and benefits of the intended study.
- 2. The length of study and the likely follow-up required.
- 3. Alternatives to the proposed study. (This will include available standard and investigational therapies. In addition, patients will be offered an option of supportive care for therapeutic studies.)
- 4. The name of the investigator(s) responsible for the protocol.
- 5. The right of the participant to accept or refuse study interventions/interactions and to withdraw from participation at any time.

Before any protocol-specific procedures can be carried out, the consenting professional will fully explain the aspects of patient privacy concerning research specific information. In addition to signing the IRB Informed Consent, all patients must agree to the Research Authorization component of the informed consent form.

Each participant and consenting professional will sign the consent form. The participant must receive a copy of the signed informed consent form.

If modifications are made according to local requirements, the new version has to be approved by AstraZeneca.

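### Section 6.2 ties contraception to the undefined duration of the study and sets no period after the last dose; if the study ends at removal, a fertile patient may stop while bicalutamide is at steady state

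*Combined protocol and SAP*

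**What the plan says.** The contraception condition is in section 6.2: "If fertile, the patient agrees to use an effective method to avoid pregnancy for the duration of the study". Neither 6.2, section 5.1 nor Appendix A gives a period after the last dose.

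The end of the study is not defined for this purpose, and the text points two ways.

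- **Ending at removal.** Section 10.0 places the end-of-study evaluation at that moment: "At the time patients are removed from study, laboratory and clinical evaluations to assess adverse events (AEs) will be performed". Section 4.3 continues the drug until a withdrawal criterion is met, so for progression the end of treatment and withdrawal coincide. The Time and Events Schedule labels the removal visit as study termination and puts resolution of adverse events in a separate column. Section 17.2.5, on post-study events, adds: "However, investigators are not obligated to actively seek adverse events in former study participants".
- **Ending later.** Section 10.0 says adverse events starting "up to 30 days after the last dose of bicalutamide, must be followed until the AE has resolved or stabilized". Section 11.2.2, in generic wording, lists the study phases as "run-in, treatment, washout, follow-up".

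Section 18.1 says the consent form covers "The length of study and the likely follow-up required". The consent pages are not in the text available for this review.

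On treatment, section 9.2 says: "Therapy will continue until disease progression or unacceptable toxicity". Section 13.0 opens with "Patients will be removed from the study if any of the following conditions apply" and lists progressive disease, with no washout before removal.

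**The concern.** The protocol already treats avoiding pregnancy during exposure as a condition of entry. Exposure outlasts the last tablet, but the contraception rule may not.

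Appendix A places bicalutamide in Pregnancy Category X and advises against use in women who may become pregnant. In rats, hypospadias in male offspring occurred at every dose given to pregnant females, so no safe level is known. The visible schedule has one pregnancy test, within 72 hours before the first dose.

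If the study ends at removal, a fertile patient taken off for progression while dosing can follow 6.2 to the letter and stop contraception the same day. What is at stake is participant and fetal safety. The response rate, the sample size and the error rates are not affected.

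**Working it through.** The plan has no figure of its own for a post-dose period, so there is none to reproduce. The check asks how much drug is present at removal and how fast it clears.

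**Inputs**

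- Half-life in men: mean 5.8 days, SD 2.29 (section 5.1; Appendix A, Table 1). Upper value used: 5.8 + 2 × 2.29 = 10.38 days. Appendix A reports 10.4 days in four patients with severe liver disease.
- Dose: 150 mg daily, with reductions to 100 mg and 50 mg (section 11.3.5).
- First scheduled tumor assessment: 12 weeks ± 2 weeks, i.e. day 70 to 98 (section 10.0).
- Longest dose hold before removal for toxicity: 14 days (section 4.3).
- Lowest rat dose tested: plasma level about 2/3 of the human level, where the human reference is 50 mg/day (Appendix A, Contraindications and footnote).
- Section 3.2 reports that steady-state concentration departs from linearity above 50 mg/day.

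First-order kinetics are assumed throughout, with half-life h.

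**Step 1. Level at removal.** Share of steady state after t days of dosing = 1 − 2^(−t/h).

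- Day 70, h = 10.38: 1 − 2^(−70/10.38) = 99.1%. It is higher at h = 5.8.
- Progression may be found before the first scan. At day 28 the share is 96.5% (h = 5.8) or 84.6% (h = 10.38).

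**Step 2. Exposure relative to the lowest rat level.** Take the human level at 50 mg as 1, so the rat level is 2/3. If concentration does not rise above the 50 mg value, the level at 150 mg is 1. If it is fully proportional to dose, it is 3, which is a ceiling given the non-linearity.

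| Dose | Human level | Ratio to 2/3 |
|---|---|---|
| 150 mg | 1 to 3 | 1.5 to 4.5 |
| 100 mg | 1 to 2 | 1.5 to 3.0 |
| 50 mg | 1 | 1.5 |

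**Step 3. Days to fall to the rat level from 150 mg.** Days = log2(ratio) × h.

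- h = 5.8: 0.585 × 5.8 = 3.4 days; 2.170 × 5.8 = 12.6 days.
- h = 10.38: 0.585 × 10.38 = 6.1 days; 2.170 × 10.38 = 22.5 days.

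**Step 4. Removal after a full 14-day hold.** Share left = 2^(−14/h): 18.8% (h = 5.8) or 39.3% (h = 10.38). The ratio of 1.5 to 4.5 becomes 0.28 to 0.84, or 0.59 to 1.77. The steady-state statement therefore applies to removal during dosing and not to removal after a hold.

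**Step 5. What 30 days achieves.**

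- h = 5.8: 2^(−30/5.8) = 2.8% left; 30/5.8 = 5.2 half-lives.
- h = 10.38: 2^(−30/10.38) = 13.5% left; 30/10.38 = 2.9 half-lives. Five half-lives would be 5 × 10.38 = 51.9 days.

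Five half-lives is a common convention and is not taken from the protocol.

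**The case against.** The strongest reply is that 6.2 may already mean what it should. The term is undefined, the schedule provides examinations and bloods in the adverse-event resolution column after the termination visit, and follow-up of adverse events runs to at least 30 days after treatment. If a patient became a former participant on the day of removal, the statement in 17.2.5 that events need not be sought would sit awkwardly with that follow-up. On this longer reading, the 30 days proposed here is already covered. The consent form may also state an interval, and its absence from the available text cannot be held against the plan.

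This stands as a reason to keep the point conditional. It does not remove it. The follow-up provisions concern adverse events and say nothing about contraception. Section 17.2.1 follows patients to the later of the end of study and 30 days after treatment, which allows the study to end before those 30 days are over. An interval in the consent would reduce the consequence but leave 6.2 unclear.

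The second reply is that the figures do not measure harm, and that is right. The rat effect followed dosing of pregnant females, whereas the case here is conception while exposure falls, for which the documents give no data. The lowest rat dose is not a safety threshold. Half-lives come from men, and the 4.5-fold ratio and the 10.38-day half-life are upper values. The number of fertile patients among the 28 is unknown, and the scenario requires one who stops contraception at once and conceives during washout.

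Finally, no standard in the documents is breached: section 5.1 and Appendix A give no post-dose period either. This is a gap in 6.2 and not a conflict between texts.

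**Conclusion.** The concern holds as a low-cost safety clarification, worth considering, with medium confidence. Section 6.2 gives no contraception period after the last dose, and ending at removal is the more natural reading of the visible text.

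On that reading, a patient removed while dosing at or after the first scheduled scan is above 99% of steady state. Her exposure is about 1.5 to at most 4.5 times the lowest rat exposure tested, and takes about 3 to 13 days to fall to that level at the mean half-life, or 6 to 23 days at the mean plus 2 SD. On the longer reading, the edit only makes the intended meaning explicit.

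The result rests on first-order kinetics, half-lives measured in men, and a 150 mg exposure bounded between no rise and full proportionality above 50 mg. It describes exposure; the fetal risk itself cannot be sized.

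**What to change.** In section 6.2, replace the reference to the length of the study with: *during treatment and for at least 30 days after the last dose of bicalutamide*. Repeat this in the end-of-study instructions in section 10.0, and in the consent form if it does not already say so.

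Thirty days is about five mean half-lives and matches the adverse-event window already in section 10.0. Clinical pharmacology should confirm the interval and may prefer about 52 days, which covers five half-lives at the mean plus 2 SD.

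The cost is one sentence and its repeats, with no new visit, test or change to the sample size. Fertile patients would use contraception for about 30 more days, or longer if the longer interval is chosen.

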6.3 Subject Exclusion Criteria

A patient will not be eligible for treatment on this study if any of the following criteria apply:

- Concurrent chemotherapy, hormonal therapy or biologic therapy is being administered to treat breast cancer.
- Serious intercurrent medical or psychiatric illness, including serious active infection.

IRB#: 07-022A(13)

- History of other malignancy within the last five years, which could affect the diagnosis or assessment of breast cancer (except non-melanomatous skin carcinoma).
- Patients who have received an investigational drug within the previous 3 weeks.
- Patient is currently enrolled in another clinical study in which investigational therapies are administered. In addition, a patient may not enroll in such clinical trials while participating in this study.

7.1 RECRUITMENT PLAN

Patients will be recruited for enrollment on this trial primarily through referrals from their primary oncologists. Efforts will be made to enroll women from a diversity of ethnic and socioeconomic backgrounds. There will be no payments made to participants or physicians for participation in this study. Prior to enrollment on the study, the physician will discuss the study protocol in detail with the patient, including possible toxicities. An informed consent will be reviewed by the physician with the patient.

Androgen Receptor Testing:

If a patient wishes to undergo androgen receptor testing on the protocol, an informed consent will be signed prior to reviewing pathologic specimens for AR status. Androgen receptor testing may be performed using the Dako antibody, catalog number M3562, Animal/Clone AR441 (antibody dilution of 1:300 with citrate buffer pretreatment). The pathology specimen submitted for AR testing can be from either the primary or the metastatic site.

[name] and team at MSKCC Department of Pathology will verify the invasive breast cancer is AR positive. Fewer than 10 unstained slides or a tumor block will be accepted if that is all that is available. I

7.2 For participating sites sending pathology specimens to MSKCC for AR testing

Participating sites must send unstained slides to MSKCC for AR testing. All specimens submitted to MSKCC for AR testing must have previously tested ER(-)/PR(-) locally. ER, PR and AR are considered positive if greater than 10% of cell nuclei are immunoreactive. [name] and team at MSKCC Department of Pathology will verify the invasive breast cancer is AR positive. If the patient is AR (+), the MSKCC Department of Pathology will verify the specimen is ER(-)/PR(-). If the patient is AR (-), the patient is ineligible and the study staff will take steps to register the patient as ineligible.

Pathology specimens may be requested from either the primary or the metastatic site. Sites must request 10 unstained slides to send to MSKCC. Fewer than 10 unstained slides or a tumor block will be accepted if that is all that is available. Specimen submissions are to be shipped with an accompanying pathology report and the tumor tissue shipment form provided by the 07-022 MSKCC research staff using the MSKCC issued patient ID. The MSKCC study staff must be notified of all shipments. Shipments cannot be accepted on weekends. All shipments should be directed to the address listed on the tissue sample shipment form. This tissue will also be used for

correlative studies as discussed in section 10.0

